In terms of seizures, all rTMS sessions will be conducted by the PI ([name]) who is (1) a board certified neurologist, (2) has been trained in the safe and efficient administration of TMS (through a course offered at the Berenson-Allen Center for Non-Invasive Brain Stimulation at the Beth Israel Deaconess Medical Center) and (3) is trained in basic life support and in the recognition and treatment of convulsions, syncope and other medical/neurological emergencies. In addition, a fully equipped and regularly checked crash cart will be available at all sites where TMS stimulation will occur. This emergency equipment includes oxygen supply, IV line supplies, and emergency medications (e.g. benzodiazepines) in the event of a convulsion. Therefore, should any complication occur, rapid medical coverage for the subject will be provided, followed by Emergency Room care if appropriate. We will also monitor patients in detail during and after delivery of rTMS, using an approach drawn directly from suggested guidelines.⁶⁸ Notably, there is not expected to be an increase in the risk of seizures with stimulation of the control site. In fact, stimulation of the cerebellum is much less likely to result in seizure induction. Other measures to minimize risks from TMS are listed in **Table 2**.

Risk Associated with TMS	Measures taken to prevent/minimize this risk
20-40% of subjects experience MILD headaches or neck pain	Care will be taken to administer stimulation in a comfortable neck position and to avoid unnecessary stimulation of neck/scalp muscles.
TMS produces a loud clicking sound which may cause tinnitus or rarely short-term hearing loss	Subjects will be given earplugs, which, in animal and human studies, proven effective in preventing the risk of hearing disturbance due to TMS.
TMS could induce short-term changes in memory, attention and other cognitive functions	This is a theoretical risk, as none of the safety studies conducted has found such side effects.
Acute psychiatric effects such as mania and delusions have been described in patients with medically refractory depression or bipolar disorder who received rTMS. This seems to be a rare complication of rTMS (incidence <0.15% of patients).	Mania and delusions arising from TMS have not been described in purely schizophrenic cohorts, e.g. those without a comorbid affective disorder. Subjects will undergo a brief rTMS side effects questionnaire after rTMS to assess for these rare effects.
Concentration/memory deficits which are exceedingly scarce.	Subjects will undergo a brief questionnaire after every rTMS session to assess for these rare effects.

Table 2. Risks associated with TMS and measures to prevent them

Risks Attributable to PET:

- Venipuncture:** An intravenous catheter will be placed for this study to inject the FDG radioligand. FDG injection will be administered by a licensed nuclear medicine technologist. All safety procedures related to venipuncture (e.g. minimization of bleeding, bruising and infection) will be strictly adhered to and venipuncture will be carried out by an experienced technician. As such, subjects are expected to feel transient discomfort at the time of venipuncture. There is also the risk of slight bruising at the sight of venipuncture. Bleeding or infection risks (e.g. cellulitis) are possible following IV placement, but these are exceedingly rare.
- Radiation exposure:** The radiation exposure in this study will be small and there is no evidence that it represents a major health risk. We will follow the safety standards put forth by the Radioactive Drug

Research Committee (RDRC) and the Massachusetts General Hospital Radiation Safety Committee. As is the convention for receiving FDG-PET, it will not be the total number of scans a subject has, but the total amount of radiation exposure per year that will serve as the limiting factor. According to RDRC policy, adult research subjects should be limited to a total of 50 milliSieverts (mSv) of radiation dose per year. It is estimated that each FDG scan results in a whole body radiation exposure of 3.5mSv per scan. This would amount to a total of 10.5mSv of exposure per year for the majority of subjects (who will each undergo three FDG-PET scans) and 14mSV of exposure per year for subjects who agree to undergo an optional fourth study visit. Notably, exposure is limited to this amount because scanning will occur on an MRI-PET scanner, and not a CT-PET scanner. Careful monitoring of a subject's recent radiation exposures will occur, and subjects will be prohibited from participation if they have received radiation for any other study in the past 12 months. If subjects have participated in other research studies in the past 12 months that have involved radiation exposure, they will be asked to inform the investigators or study staff (by placing a check mark on the consent form verifying that they have or have not been exposed to other radiation in the past 12 months). If it is determined that the prior radiation exposure exceeds our current guidelines (i.e. 15 mSv/year) the subject will not be enrolled in this study.

We will use FDG purchased through commercial sources, specifically through PETNet and Cardinal Health. We will follow the safety standards approved by the Radiation Safety Committee for the use of radioligands. The IV injection will be administered either by a physician or by a trained technician. There is an extremely small risk of allergic reaction to FDG. Should there be an adverse event, [name] will be responsible for communicating with the IRB within the stipulated time frame.

Possible risks associated with combined MRI-PET: There are no foreseeable additive risks from combining PET with MRI. The U.S. Food and Drug Administration (FDA) recently gave the first regulatory clearance of a hybrid PET/MRI scanner in the U.S. However, it should be noted that the specific combined PET/MRI machine that will be used as part of this study is not FDA approved.

Risks attributable to behavioral testing: The questionnaires employed as part of the study may cause some subjects to feel frustrated, bored or upset. It might also cause them to feel dysphoric as it may remind them of their clinical depressive symptoms. Subjects will be told that they may stop at any time during the testing.

Possible risks of delaying treatment in MDD subjects: MDD subjects may or may not have a treating psychiatric provider during their participation. If the subject does have a current provider, the PI will correspond directly with the subjects' psychiatric provider after seeking formal permission from the subject to do so (in the form of a signed medical release form to discuss his/her care supplied by said provider's office). This will allow the PI to (1) discuss maintenance strategies for the subject during their pre-treatment phase, (2) report worsening of the patient's mood to the provider and (3) receive reports from said provider about clinical deterioration. Maintenance strategies might include, for example, having MDD subjects undergo brief interpersonal therapy (IPT), either through the outpatient Psychiatry department at BWH or directly with their provider.

However, in some cases an MDD subject may refuse to have a psychiatric provider and refuse to undergo treatment for their depression (even after the risks of doing so are explained to them by the PI). That is, they may have decided to not pursue pharmacotherapy or psychotherapy to treat their depression. In these cases, treatment would not be "delayed," as the subject never intended it to be started. For these subjects, the PI (a board certified psychiatrist) will still monitor MDD subjects in the following ways to assess symptom worsening during their study participation. First, he will directly ask subjects at each of their three visits about possible symptom worsening. Secondly, and more objectively, this will be assessed by performing a HAMD questionnaire at each of the three study visits. Third the PI will provide brief patient education on Major Depression, specifically with respect to common symptomatology, theories as to the biological basis of the disorder and treatment options. Fourth, the PI will encourage that they seek treatment in the form of psychotherapy during the study and with psychotherapy and/or pharmacotherapy after their study participation ends.

In addition, subjects with MDD who experience a 20 percent increase in their HAMD rating scores during the course of the study will be removed from the study and referred to a regular psychiatric clinician for the institution of prompt treatment. As mentioned, this will be assessed by performing a HAMD at each of the three study visits.

Depressed patients will be evaluated at each study visit with the Columbia Suicide Severity Rating Scale (CSSRS) as well as the HDRS. If subjects report active suicidal ideation (SI) on either scale they will be removed from the study. Of note, this course of action will be taken if a subject endorses active suicidal ideation at any visit, even if their HDRS score has not increased by 20% from their last visit. Suicide risk in these individuals will be further probed by examining their CSSRS responses. If the risk of suicide is deemed high and/or imminent (e.g., if the subject endorses frequent active SI, has intent and/or plan for self-injury) the subject will be immediately referred to the Emergency Department at MGH. In these cases of extreme concern, subjects will be taken to the ED with a security escort and may have to be taken against their will. If the subject is determined to have SI but to not be an imminent risk for suicide, it will be suggested that they contact the Boston Emergency Services Team (BEST), which is jointly operated through MGH and Boston University and which is well equipped to provide acute care and to facilitate rapid referrals to psychiatric providers. Information on contacting the BEST team will be provided on the MDD resource sheet. Obviously, if the subject has an established psychiatric provider, they will be encouraged to contact that individual immediately as well.

VIII. POTENTIAL BENEFITS

It is not expected that individuals participating in this study will benefit directly from it, other than through financial compensation. Furthermore, MRI scans being used are NOT sufficiently clinically diagnostic to detect pathology. However, if a pathological finding is suspected, the subject will be referred for further neurological and/or radiological work-up.

This work will better elucidate how intrinsic networks and their dynamics are altered in MDD. It will also assess how rTMS, or other neuromodulatory strategies, create the formation of more adaptive configurations. In turn, this will pollinate future trials that optimize MDD treatments through selective targeting of intrinsic networks.

IX. MONITORING AND QUALITY ASSURANCE

The Principal Investigator (PI), [name] and his staff will have the responsibility for continually monitoring all aspects of the studies, including adverse events (AEs), and for reporting AEs according to the PHRC guidelines. Adverse effects will be collected from the start of the experimental protocol to the end of study participation. All adverse events, regardless of attribution to rTMS, to MRI scanning or to PET scanning or any other study associated procedure or questionnaire, will be collected and recorded using standard adverse event forms approved by the Partners IRB. Participants will be asked in an open-ended way about the presence of any such events. Also, a standard questionnaire for TMS-related adverse effects (see attachment) will be performed in the period after every rTMS session. Intensity of each adverse event will be graded as mild, moderate or severe. Events will be medically evaluated where appropriate, including testing and referral.

All study investigators attest that they have read the adverse event definitions provided by the PHRC and that they have undergone the required training in the protection of human subjects. The PI understands the responsibilities and reporting requirements for the PHRC. Adverse events and unanticipated problems will be reported to the IRB per PHRC reporting guidelines.

Descriptions of AEs and unanticipated events which are not AEs will include: detailed descriptions of the events themselves, descriptions of whether the event was expected or unexpected, descriptions of the severity and frequency of the events, determinations as to whether the event is related or possibly related to study procedures, determinations as to whether continuation in the study places subjects at an increased risk of harm, and whether changes to the research or other corrective actions are warranted.

To safeguard confidentiality and the privacy of protected health information, each study subject will be assigned a unique code number. A separate file linking the patient's name with study number and identifiers will be kept in a password-protected data file, accessible only by the study investigators. All study forms will be kept in secure locked file cabinets. The study investigators will assume full responsibility to maintain the confidentiality of all data. All study results will be presented only as statistical aggregates that will neither identify, nor permit identification of, individual subjects.

[name], the principal investigator, will review the accuracy and completeness of the data and adherence to the PHRC approved protocol on a continuing basis. Guidelines regarding Data and Safety Monitoring Plans and Quality Assurance and Adverse Event Reporting Guidelines will be followed at all times.

X. REFERENCES

1. Mayberg, H.S., *Limbic-cortical dysregulation: a proposed model of depression*. J Neuropsychiatry Clin Neurosci, 1997. **9**(3): p. 471-81.
2. Drevets, W.C., et al., *Subgenual prefrontal cortex abnormalities in mood disorders*. Nature, 1997. **386**(6627): p. 824-7.
3. Krishnan, V. and Nestler, E.J., *Linking Molecules to Mood: New Insight Into the Biology of Depression*. Am J. Psychiatry, 2010. **167**(11): 1305–1320.
4. Mayberg, H.S., *Modulating dysfunctional limbic-cortical circuits in depression: towards development of brain-based algorithms for diagnosis and optimised treatment*. Br Med Bull, 2003. **65**: p. 193-207.
5. Mayberg, H.S., *Defining the neural circuitry of depression: toward a new nosology with therapeutic implications*. Biol Psychiatry, 2007. **61**(6): p. 729-30.
6. Ressler, K.J. and H.S. Mayberg, *Targeting abnormal neural circuits in mood and anxiety disorders: from the laboratory to the clinic*. Nat Neurosci, 2007. **10**(9): p. 1116-24.
7. Seminowicz, D.A., et al., *Limbic-frontal circuitry in major depression: a path modeling metanalysis*. Neuroimage, 2004. **22**(1): p. 409-18.
8. Greicius, M.D., et al., *Resting-state functional connectivity in major depression: abnormally increased contributions from subgenual cingulate cortex and thalamus*. Biol Psychiatry, 2007. **62**(5): p. 429-37.
9. Sheline, Y.I., et al., *Resting-state functional MRI in depression unmasks increased connectivity between networks via the dorsal nexus*. Proc Natl Acad Sci U S A, 2010. **107**(24): p. 11020-5.

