- A. **MDD patients: 25 patients** (ages 18-50) with unipolar MDD (single episode or recurrent) will participate. We will specifically recruit unmedicated patients. At enrollment, patients must be medication free for a period consistent with four half-lives of the drug in question (e.g. 4 weeks for fluoxetine). Diagnoses of MDD will be made by each patient's referring physician, or, in the case that there is not a referring physician, will be made by the PI (a board certified psychiatrist) with DSM-IVR criteria using the Structured Clinical Interview (SCID).⁶⁵ Patients will also be required to score ≥ 18 ⁷ on the 24 item version of the Hamilton Depression Rating Scale (HDRS).²⁴ All psychometric assessments will be performed by a trained technician. Patients with any of the following issues will be excluded: bipolar disorder, schizoaffective disorder, active suicidal ideation, or any history of psychosis. Given the high co-morbidity, concurrent anxiety disorders will be allowed, provided MDD is the major diagnostic consideration.
- B. **Healthy subjects: 25 healthy controls** (ages 18-50) will also be recruited. These subjects will be matched to MDD patients on the basis of age, gender and ethnicity. Controls must score ≤ 8 on the HDRS. These subjects must not meet criteria for any Axis I disorder (confirmed by DSM-IV criteria and by the SCID questionnaire), have no formal history of these, and must not be on any psychotropic medications.
- C. **Exclusion Criteria (All Subjects)**
 1. A history of serious concurrent medical or neurological illness, especially any patient with a known space-occupying lesion in the brain/skull.
 2. Concurrent substance use, abuse or dependence.
 3. Contraindications to receive MRI scanning including, but not limited to the presence of metallic or ferromagnetic implants (e.g. pacemaker, defibrillator, vagal nerve stimulator, implantable pump, metallic tattoos and/or make-up, surgical aneurysm clips, etc.); or severe claustrophobia.
 4. Contraindications to undergo PET scanning, e.g. a history of receiving radiation exposure with PET within the past 12 months.
 5. Contraindications to receiving TMS, specifically a history of seizures/epilepsy in the subject or in a first-degree relative or history of unexplained syncope.
 6. Any subject who is pregnant (as assessed by a STAT quantitative serum hCG test) or currently lactating.

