 3. Patients of [name] (co-investigator) who present to the MGH Depression Clinical Research Program (DCRP) with symptoms of major depression.

In the latter two cases, the PI will strongly emphasize that study participation is voluntary and that subjects' decisions to not participate will in no way affect their care with said investigator or their future care at any Partners institution.

Once identified as potentially eligible, subjects will undergo the aforementioned telephone screening/email assessments with the PI to further delineate their eligibility.

IV. SUBJECT ENROLLMENT

- A. Subjects will be randomized as to the order of the TMS sessions they undergo (there are two types of sessions in which one of two sites on the prefrontal cortex is stimulated). The order of these sessions will be counterbalanced across subjects. In other words, we will alternate between the two types of sessions and will have equal numbers of subjects having undergone a particular order of sessions. This will allow us to account for order effects.

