Study procedures will first consist of completion of study questionnaires followed by experimental procedures. In order to ensure eligibility to participate, all subjects will complete a SCID and HDRS rating scale. These will confirm the existence/absence of major depression and the absence of comorbid psychiatric conditions. Other exclusionary criteria will be screened via non-structured clinical interviews. A subject's eligibility for safely receiving rTMS, PET and fMRI will be assessed by filling out the appropriate screening forms (see attachments). All of these procedures will be performed by [name] (PI) who is trained in administering these instruments and screening forms. Finally, women of childbearing age will undergo a STAT quantitative serum hCG to ensure that they are not pregnant.

C. Aim 1 and 2 Experimental Procedures

50 subjects (25 MDD patients and 25 matched controls) will each undergo three experimental visits. In addition, of these subjects a subset (no more than five) will be given the option to undergo a fourth experimental visit. During the first study visit, consent will be obtained. Following this, subjects will be assessed for eligibility by

Fig 5.

Experimental timeline. Baseline fMRI/PET done on visit 1. Subjects return days later for 2-3 more visits in which they have fMRIs before rTMS and fMRI/PET afterwards.

screening procedures mentioned above. If they are considered eligible, they will undergo a baseline scan during this visit.

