Specifically, subjects will undergo simultaneous resting-state (fcMRI)/FDG-PET imaging *without* rTMS at this first visit. The baseline PET session will serve as a comparison for changes in rCMRglu following rTMS. Critically, strong evidence supports the test re-test reliability across FDG-PET scanning sessions separated in time, provided that scanning parameters remain identical.⁷¹⁻⁷⁴ Therefore, observed metabolic changes after rTMS will be attributable to the stimulation, and will be deemed unlikely to occur as a result of inherent variability across scanning sessions. Baseline fcMRI data will serve the purpose of creating functional connectivity maps from a sgACC seed. Similar to how lpIPL was designated in Eldaief et al.¹⁴, these maps will be used to establish two cortical targets for rTMS in DLPFC: one which is positively correlated to sgACC, and another which is anticorrelated to sgACC^{21,22} (**Fig 1**). After their baseline visit, subjects will return for the first of two rTMS sessions in which they will receive 20Hz stimulation to either the positively or negatively correlated left DLPFC region. They will then return for a third session in which the alternate region is stimulated (thus enabling a within-subject design). Subjects will be randomized to a given session order, and this order will be counterbalanced across subjects. It is expected that all three visits will be completed within two months from the time of enrollment. The experimental timeline for the rTMS sessions is depicted in **Fig 5**. Immediately before stimulation subjects will be rapidly scanned with resting-state fMRI *without* PET (for approx. 25 minutes). After this, they will fill out a brief (1 min) visual analog scale in which they rate sadness, anxiety, energy, concentration, happiness, anger and disgust on a scale of 0-10. They will then be taken into a room immediately adjacent to the scanner for rTMS (i.e. constituting “off-line” stimulation⁷⁵). Subjects will be injected with FDG concurrent to the onset of rTMS. After rTMS they will again complete the mood analog scale. They will then be promptly returned to the scanner room for PET/fcMRI (within ~5 min) so as to acquire BOLD data as soon as possible after rTMS.¹⁴ Dynamic PET acquisitions will correspondingly begin at this time (e.g. at approx. 30-35 min post FDG injection), and emission data will be collected for the next 45 min.

	Visit 1	Visit 2	Visit 3	Visit 4
Obtainment of Consent	X			

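### Session order is called randomised but defined as alternation, and it is not balanced within diagnosis, which leaves the MDD-versus-control comparison of the site contrast open to a visit effect

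*Protocol*

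**What the plan says.** Protocol section IV (Subject Enrollment), A, first states: "Subjects will be randomized as to the order of the TMS sessions they undergo". It adds: "The order of these sessions will be counterbalanced across subjects". It then explains what this means in practice: "we will alternate between the two types of sessions and will have equal numbers of subjects having undergone a particular order of sessions". The purpose given is: "This will allow us to account for order effects".

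Section V.C (Aim 1 and 2 Experimental Procedures) describes the same step without alternation: "Subjects will be randomized to a given session order, and this order will be counterbalanced across subjects". It also makes the design a crossover of the two sites: "They will then return for a third session in which the alternate region is stimulated (thus enabling a within-subject design").

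On numbers, section V.C states: "50 subjects (25 MDD patients and 25 matched controls) will each undergo three experimental visits". Section III.B says of the controls: "These subjects will be matched to MDD patients on the basis of age, gender and ethnicity".

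Section VI (Biostatistical Analysis) lists three main fcMRI measures: the change in z, the difference in that change between stimulation conditions, and the comparison of that difference between subject groups, with MDD versus controls as the example. The tests it names are t-tests, with no term for order or visit.

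The principal investigator carries out the telephone or email screen (section III, recruitment), obtains consent (IV), does the eligibility procedures (V.B) and conducts all rTMS sessions (VII).

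**The concern.** There are two separate problems.

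**The method contradicts its name.** Section IV.A names randomisation and then defines it as alternation. Section V.C names only randomisation and counterbalancing. These are different allocation methods for the same step. Under alternation, the person who enrols knows the next order before the next subject consents. A report that followed IV.A and called the order randomised would be inaccurate.

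**Balance is set over the wrong unit.** The stated aim is to deal with order effects. Equal totals over 50 subjects achieve this for the pooled comparison of the two sites. They do not achieve it for the comparison of MDD with controls, because a visit effect cancels there only if the two orders are split alike in the two groups. Neither section ties the balance to diagnosis. Hypotheses 1.3 and 2.4 both rest on a group comparison.

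**Working it through.** **Inputs.** 50 subjects, 25 per diagnosis (V.C). Equal numbers per order over all subjects (IV.A). Each subject receives both sites (V.C). The size of any visit effect and the enrolment sequence are not given, so both are treated as assumptions.

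**Step 1: the plan's own promise.** 50 / 2 = 25, so 25:25 overall is achievable exactly. Within a diagnosis 25 / 2 = 12.5, so the best split is 13:12. Mirrored splits of 13:12 and 12:13 still total 25:25.

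**Step 2: how a visit effect enters.** Call the sites A and B. Let P be the additive shift in the change score from Visit 2 to Visit 3, and D a subject's site contrast (change at A minus change at B), with true value τ.

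- Order A then B: D = τ − P.
- Order B then A: D = τ + P.
- Mean of D in a group in which a fraction f has order A then B: τ + P(1 − 2f).
- Pooled over all subjects with f = 0.5: the P term is zero.
- MDD minus controls: absolute bias = 2 × P × gap, where gap = |f(MDD) − f(controls)|.

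**Step 3: one alternating list over all 50, diagnoses arriving at random.** The number of MDD patients in one order is hypergeometric (50, 25, 25), SD 1.79. With the total fixed at 25:25, controls mirror the MDD split, so gap = |2k − 25| / 25 for k MDD patients in one order.

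| MDD split (controls mirrored) | Gap | Bias | Chance of this split or worse, either direction |
|---|---|---|---|
| 13/12 | 0.04 | 0.08 P | 1.00 |
| 14/11 | 0.12 | 0.24 P | 0.57 |
| 15/10 | 0.20 | 0.40 P | 0.26 |
| 16/9 | 0.28 | 0.56 P | 0.089 |
| 17/8 | 0.36 | 0.72 P | 0.023 |

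**Step 4: other sequences the protocol leaves open.**

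- One group enrolled entirely before the other: the list gives 13/12 and then 12/13, gap 0.04, bias 0.08 P.
- Patient and control enrolled strictly in turn: 25/0 and 0/25, gap 1.0, bias 2 P, with order and diagnosis coinciding.

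**Step 5: scale, for assumed values of P.** Section III.D sizes the study on a change of 0.15 z.

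| Assumed P (z) | Gap 0.04 | Gap 0.20 | Gap 1.0 |
|---|---|---|---|
| 0.05 | 0.004 | 0.02 | 0.10 |
| 0.075 | 0.006 | 0.03 | 0.15 |
| 0.15 | 0.012 | 0.06 | 0.30 |

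**The case against.** The case against is substantial, and most of it limits the size of the point.

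- **Equal numbers.** A reader might infer that the protocol promises equal numbers that 25 per group cannot deliver. It does not: the promise covers all subjects, and 50 divides into 25:25. The odd group size costs at most 0.08 P.
- **Pooled or separate lists.** The text does not say whether alternation runs over one list or separately by diagnosis. Separate lists would give 13/12 in each group. So balance within diagnosis is not secured, rather than shown to be absent.
- **Total confounding.** A reader might infer from the matching of controls that patients and controls are enrolled in turn. Matching is only on characteristics, and recruitment uses separate advertisements plus extra clinic sources for patients. The 2 P case is an assumption, and so is the benign 0.08 P case.
- **Source of the 26%.** This comes from not stratifying, not from alternation itself. The SD of the gap is 2 × 1.786 / 25 = 0.143 in step 3, and √(2 × 0.25 / 25) = 0.141 under unstratified coin-flip randomisation. The same model also gives 14/11 or better 74% of the time.
- **Predictability.** A reader might infer that foreknowledge lets the investigator choose who gets which site. Each completer receives both sites, so only the sequence could be influenced, and the person stimulating must know the site anyway.
- **Meaning of P.** The fcMRI outcome is a pre-to-post change within a session, so drift in connectivity level between visits cancels. Only a shift in the response to rTMS would bias it. This defence does not reach PET, where post-rTMS scans are compared with the Visit 1 baseline.
- **Analysis.** An SAP might add an order term, which would remove an additive visit effect unless order and diagnosis coincide.
- **Wording.** The sentence speaks loosely of alternating session types. Read with its promise of equal numbers per order, it most naturally means alternation from subject to subject.

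What stands after this is the contradiction between randomisation and alternation, and the lack of any stated protection for the group comparison.

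**Conclusion.** The point holds at moderate severity. Section IV.A defines a randomised order as alternation, section V.C does not, and neither balances order within diagnosis. The pooled site contrast is protected from an additive visit effect by the 25:25 split. The exposed result is the MDD-versus-control comparison of that contrast.

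Its size depends on two things the protocol does not state. With one list and random arrival of diagnoses, the chance of a bias of at least 0.40 P is 26%, which is 0.02 to 0.06 z or more for an assumed P of 0.05 to 0.15 z. Across the enrolment sequences considered, the bias runs from 0.08 P to 2 P. The documents do not show that a visit effect exists or that either extreme sequence will occur, so this is an avoidable exposure and not a demonstrated bias.

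**What to change.** Delete the alternation sentence in section IV.A and make IV.A and V.C say the same thing. Suggested text: *Within each diagnostic group, session order is assigned from a computer-generated list in randomly permuted blocks. The list is held by existing study staff who neither enrol nor stimulate, and each assignment is revealed after the Visit 1 scan is complete. The target is 13:12 in one group and 12:13 in the other.*

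Generate the two lists together so that their end points mirror each other. That keeps the promised equal numbers overall (25:25) and limits the bias in the group comparison to 0.08 P at full enrolment.

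The cost is one protocol sentence and one generated list, with no added subjects, visits or staff. It should be in place before enrolment, because analysis cannot separate order from diagnosis if the two coincide.
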